9.2 Sample Size and Randomization

Approximately 360 subjects will be enrolled in a randomization ratio of 1:1:1, with each subject assigned to the rexlemestrocel-L alone, rexlemestrocel-L + HA, or saline control group. Randomization will be stratified by study site and opioid use at baseline (opioid users vs. opioid non-users).

9.3 Analysis Analysis sets

The classification of subjects into each of the following analysis analysis sets will be determined prior to database lock for the 24-month data analysis and prior to the 36 month longer-term follow-up analysis.

9.3.1 All Enrolled Subjects Analysis Set

All subjects who signed the informed consent are included in the All Enrolled analysis set. The All Enrolled Subjects analysis set will be used for summarizing subject disposition.

9.3.2 Intent-to-Treat (ITT) Analysis Set

The ITT analysis set includes all subjects who are randomized, regardless of whether or not the subject is treated, or post-treatment measurements are performed. In these analyses, subjects will be assigned to treatment according to randomization (not actual treatment received). The ITT analysis set will be used for summarizing demographics, baseline characteristics, surgical procedures and treatment exposure. The ITT analysis set will be used as the primary analysis set for all primary and secondary efficacy analyses. As sensitivity, the efficacy analyses will also be performed on the Full Analysis Set, the As Treated and the Per Protocol analysis sets, as defined herein.

9.3.3 Full Analysis Set (FAS)

The FAS analysis set includes all subjects who are randomized and treated or randomized with an attempt to administer treatment (i.e. subjects taken to procedure room to receive treatment whether administered or not). In these analyses, subjects will be analyzed according to the treatment to which they were randomized (not actual treatment received). Subjects that were randomized but dropped out prior to attempting treatment will be omitted from the FAS analysis set.

9.3.4 As Treated Analysis Set

The As Treated analysis set includes all subjects randomized, analyzed according to the treatment that was actually administered.

9.3.5 Per Protocol (PP) Analysis Set

The per-protocol (PP) analysis set will contain all subjects in the ITT who received treatment to which they were randomized, had at least 1 post-treatment efficacy measurement (VAS and ODI), and did not experience any major protocol deviations.

Protocol deviations will be determined for all randomized subjects mainly from the clinical database and Clinical Trial Management System (CTMS) following clinical and/or medical review of subject data for relevant findings that might have an impact on the definition of the PP analysis set/ major protocol violations. Protocol deviations that occur during the study will be adjudicated by the sponsor (or designee) and categorized by severity. Protocol deviations will be classified as minor or major during a blinded review of the data prior to the lock of the database for analysis. If relevant deviations are identified, they will be designated as major protocol violations.

9.3.6 Safety Analysis Set

The safety analysis set will contain all subjects who were randomized and received treatment, and subjects will be classified according to the actual treatment received. Safety analysis set will be used for the safety analyses.

If there is any doubt whether a subject was treated or not, they will be assumed treated (randomized treatment) for the purposes of analysis.

9.4 Efficacy Endpoints

The efficacy endpoints to be assessed include:

9.4.1 Primary Efficacy Endpoint

The primary efficacy endpoint will be a composite responder analysis for Overall Treatment Success at both Study Visit 6 (12 months post-treatment) AND Study Visit 8 (24 months posttreatment), based on pain, function and post-treatment interventions:

- at least a 50% reduction from baseline in low back pain VAS score (average pain over 24 hours, in-clinic assessment); *AND*
- at least a 15 point decrease from baseline in ODI score (in-clinic assessment; AND
- no interventions at the treated level.

9.4.2 Secondary Efficacy Endpoints

If the primary analysis yields a significant result, then analyses will be performed on the following secondary efficacy endpoints in sequential order to control type I error:

- 1. **Pain Responder at both 12** *AND* **24 months**: Measured as subjects meeting at least a 50% decrease from baseline in low back pain VAS score (average pain over 24 hours) at both Study Visit 6 (12 months post-treatment) and Study Visit 8 (24 months post-treatment) with no adjudicated post-treatment intervention through Study Visit 8.
- Functional Responder at both 12 AND 24 months: Measured as subjects meeting at least a 15-point decrease from baseline in ODI at both Study Visit 6 (12 months posttreatment) and Study Visit 8 (24 months post-treatment) with no adjudicated posttreatment intervention through Study Visit 8.
- 3. Treatment Success at 24 months: Measured as subjects meeting each of the following criteria at Study Visit 8 (24 months post-treatment):
 - a. at least a 50% reduction from baseline in low back pain VAS score (average pain over 24 hours); AND
 - b. at least a 15 point decrease from baseline ODI score; AND
 - c. no interventions at the treated level
- 4. Minimal Pain Responder at 24 Months: Measured as subjects meeting low back pain VAS score (average pain over 24 hours) of 20mm or less at Study Visit 8 (24 months post-treatment) with no adjudicated post-treatment intervention through Study Visit 8.
- 5. Minimal Disability Responder at 24 Months: Measured as subjects having an ODI score of 20% or less at Study Visit 8 (24 months post-treatment) with no adjudicated post-treatment intervention through Study Visit 8.
- 6. **Time to first intervention over 24 months:** Measured as time to first post-treatment intervention at the treated level through 24 months post-treatment.

CONFIDENTIAL

Version 6.0

[figure not shown]
CONFIDENTIAL

Mesoblast

• Mean change in low back pain VAS score at 1, 3, 6, 12, 18, 24 and 36 months: Measured as mean change from baseline in low back pain VAS score (average pain over 24 hours) for all subjects within a treatment arm at each of Study Visits 3, 4, 5, 6, 7, 8, and 9, separately (corresponding to 1, 3, 6, 12, 18, 24 and 36 months post-treatment)

[figure not shown]

[figure not shown]

[figure not shown]

CONFIDENTIAL

Mesoblast

9.6 Statistical Methods

9.6.1 Demographic and Other Baseline Characteristics

Demographics and baseline characteristics will be summarized by treatment arm for the ITT and PP analysis sets, as well as presented in data listings.

Continuous variables will be summarized using descriptive statistics (number of subjects, mean, standard deviation, median, minimum, and maximum). In order to assess baseline comparability, treatment groups will be compared for all continuous variables using an ANOVA between individual treatment and control groups.

Categorical variables will be summarized using counts and percentages for each category. Treatment groups will be compared for all non-missing categorical variables using a Chi-Square test of association. Missing categories will be presented if necessary, but excluded from any tests of association.

Demographic data will include:

- Sex
- Age
- Race (White, Hispanic-White, Hispanic non-white, Black or African American, American Indian/Alaska Native, Asian, Native Hawaiian or Pacific Islander, Other)
- Smoking status (Never Smoked, Current Smoker, and Previous Smoker).

General baseline characteristics will include weight, height, and BMI, and baseline characteristics of the index level, as assessed by independent radiologist and will be listed and summarized based on the following assessments collected at the screening visit:

- Medical history, including history of disc disease (DDD) at the index level (duration of low back/limb pain)
- Spinal surgery history
- Medication history
- VAS, ODI, iPCQ, EQ-5D questionnaire

- Disc degeneration, Modified Pfirrmann score, herniation presence and score, average disc height
- Opioid user or opioid non-user at baseline.

General medical history will be listed and summarized, as well as medication history. Spinal surgery history and disease-specific history will be listed only.

9.6.2 Primary Efficacy Analysis

The Primary Efficacy Endpoint for overall treatment success (responder vs non-responder) at 12 *AND* 24 months will be summarized for each treatment by numbers and percentages. Each active treatment arm will be compared to the saline control group using a Bayesian test of superiority using non-informative Beta (0.5, 0.5) priors for each arm. An arm will be considered superior to the saline arm if there is sufficiently high posterior probability that the response rate of that arm is higher than the saline control arm. The posterior probability threshold is Bonferonni-adjusted to account for multiple comparisons. The value of the posterior probability threshold for success will be discussed in the study statistical analysis plan (SAP).

The rationale for using a Bayesian approach for the primary analysis is that we are already using Bayesian methodology for multiple imputation of missing data (see Section 9.9). Keeping the Bayesian methodology for the primary analysis ensures a consistent framework that naturally synthesizes the multiply imputed outcomes into the posterior distribution. In this way, the uncertainty due to missing data is naturally incorporated into the inference, without the cumbersome necessity of combining p-values as in a frequentist framework. The methods for handling missing data are discussed in Section 9.9.

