9. STATISTICAL CONSIDERATIONS

9.1 General Considerations

The statistical analysis plan (SAP) will be finalized and submitted to the appropriate health authorities before any interim analysis or unblinding occurs. The primary unblinded statistical analyses will be conducted by the sponsor or authorized representative after all enrolled study subjects who remain active in the trial at the time of their 24 month study visit have completed this milestone event.

Interim analyses may be performed during the course of the trial. These will be conducted by external independent statistician(s) who will be unblinded to study data. All blinded personnel and subjects will remain blinded to the results of the analyses. The integrity of the study database will be maintained as well, and no bias will be introduced to the evaluations in the study due to the conduct of these interim analyses.

The details of interim analyses are outlined in the Statistical Analysis Plan (SAP). All subjects, independent reviewers and blinded personnel interacting with subjects will remain blinded through the completion of the study.

[figure not shown]
The primary efficacy objective of the study is to demonstrate that either rexlemestrocel-L alone or rexlemestrocel-L + HA has a higher rate of treatment success—defined as 50% reduction in low back pain VAS score, 15 point decrease in ODI score, and no interventions at the treated disc—compared to the saline control arm at 12 *AND* 24 months post-treatment. The significance level for the Primary Efficacy Endpoint is adjusted for multiple comparisons of each active

treatment arm to the control group. The family-wise type I error rate will be controlled below one-sided 0.025. Additional details, including the adjusted threshold for primary analysis success, will be finalized in the SAP.

For secondary endpoints, a gatekeeping strategy will be used to maintain the overall type 1 error at overall one-sided 0.025. For all other exploratory efficacy endpoints, the significance level of two-sided 0.05 will be used for comparison between each active arm and the control group.

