9.6.3 Secondary and Other Efficacy Analyses

The same Bayesian methodology used for the primary analysis will also be used for the secondary endpoints. The Bonferroni-adjusted posterior probability threshold of 0.9875 will apply to any subsequent secondary analyses performed.

As part of the gatekeeper strategy, the evaluation will be carried out in a hierarchical fashion following the order given below. Specifically, if the primary endpoint objective is met, the secondary outcomes will be evaluated hierarchically within each arm using the posterior probability threshold of 0.9875 for each comparison, sequentially. Once a key secondary endpoint is not met at this threshold within an arm, all subsequent comparisons in that arm will be considered exploratory.

- Pain Responder at both 12 AND 24 months: Measured as subjects meeting at least a 50% decrease from baseline in low back pain VAS score (average pain over 24 hours) at both Study Visit 6 (12 months post-treatment) and Study Visit 8 (24 months posttreatment) with no adjudicated post-treatment intervention through Study Visit 8.
- Functional Responder at both 12 AND 24 months: Measured as subjects meeting at least a 15-point decrease from baseline in ODI at both Study Visit 6 (12 months posttreatment) and Study Visit 8 (24 months post-treatment) with no adjudicated posttreatment intervention through Study Visit 8.
- 3. Treatment Success at 24 months: Measured as subjects meeting each of the following criteria at Study Visit 8 (24 months post-treatment):
 - a. at least a 50% reduction from baseline in low back pain VAS score (average pain over 24 hours); AND
 - b. at least a 15 point decrease from baseline ODI score; AND
 - c. no interventions at the treated level
- 4. Minimal Pain Responder at 24 Months: Measured as subjects meeting low back pain VAS score (average pain over 24 hours) of 20mm or less at Study Visit 8 (24 months post-treatment) with no adjudicated post-treatment intervention through Study Visit 8.
- 5. Minimal Disability Responder at 24 Months: Measured as subjects having an ODI score of 20% or less at Study Visit 8 (24 months post-treatment) with no adjudicated post-treatment intervention through Study Visit 8.
- 6. Time to first intervention over 24 months: Measured as time to first post-treatment intervention at the treated level through 24 months post-treatment.

CONFIDENTIAL

Mesoblast

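### The primary test and binary secondaries 1–5 compare raw response rates without the opioid stratum, baseline VAS or baseline ODI: valid, but a cheap, low-priority efficiency gain is left unused

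*Combined protocol and SAP*

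**What the plan says.** Section 9.6.2 says that each active arm is "compared to the saline control group using a Bayesian test of superiority using non-informative Beta (0.5, 0.5) priors for each arm". An arm succeeds if the posterior probability that its response rate exceeds saline's is high enough. The stated reason for a Bayesian test is that it "naturally synthesizes the multiply imputed outcomes into the posterior distribution", which avoids combining p-values.

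Section 9.6.3 adds: "The same Bayesian methodology used for the primary analysis will also be used for the secondary endpoints". This fits the five binary secondaries. The sixth, time to first intervention, has its own log-rank test, stratified by site only. Section 9.6.3 gives 0.9875 as the secondary threshold; 9.6.2 leaves the primary value to the SAP. Section 9.1 sets the error limit: "The family-wise type I error rate will be controlled below one-sided 0.025".

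Section 9.2 says: "Randomization will be stratified by study site and opioid use at baseline (opioid users vs. opioid non-users". Section 9.6.1 lists "VAS, ODI, iPCQ, EQ-5D questionnaire" and "Opioid user or opioid non-user at baseline" among the baseline characteristics. None of these is a term in the comparison described.

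**The concern.** The sample size is fixed at about 120 per arm. If baseline pain, disability or opioid use predicts response, a comparison that uses them is more precise and needs no extra subjects or data. Under 9.6.3, one secondary missed at the threshold makes all later comparisons in that arm exploratory, so lost precision can carry forward.

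The endpoint definitions also tie response to baseline. Entry allows VAS 40–90 mm and ODI 30–90 (4.2.1). The primary requires "at least a 50% reduction from baseline in low back pain VAS score", which is 20 mm from a baseline of 40 but 45 mm from 90. The 15-point ODI fall is 15/30 = 50% of the lowest entry score but 15/90 = 17% of the highest. Secondaries 4 and 5 use absolute cut-offs of 20 mm and 20%. Reaching 20 mm needs a 50% fall from 40 but 78% from 90, so baseline may matter more there.

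**Working it through.** **Inputs.** 120 per arm (3.1). Threshold 1 − 0.025/2 = 0.9875, which reproduces the figure in 9.6.3; z = 2.241. Active rates from Phase 2 (1.6.3): 12/27 = 44.4% at the trial dose and 11/29 = 37.9% at the higher dose. The saline rate, dropout and prognostic strength are not in the public text.

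**1. Validity of the present test.** Exact enumeration of the Beta(0.5, 0.5) rule with three arms and a shared control gives family-wise error of 0.0231–0.0244 at common rates of 10–40%. That is below 0.025, with no interim looks modelled. With prognostic covariates and randomisation balanced on opioid use, simulated error per comparison was 0.0101–0.0114 against the nominal 0.0125, so ignoring the stratum is slightly conservative.

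**2. Present power, exact.**

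| Active | Saline (assumed) | Power |
|---|---|---|
| 44.4% | 15% | 99.8% |
| 44.4% | 20% | 97.1% |
| 44.4% | 26% | 78.4% |
| 44.4% | 30% | 53.8% |
| 37.9% | 20% | 80.6% |

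**3. Analytic gain.** If covariates explain a share R² of outcome variance, power ≈ Φ(Δ / (SE·√(1 − R²)) − 2.241), with SE = √[(p₀(1 − p₀) + p₁(1 − p₁))/120].

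- 44.4% v 26%: SE = √[(0.1924 + 0.2469)/120] = 0.0605. Power is Φ(0.807) = 79.0%, then 81.2% at R² 5% (+2.2) and 86.5% at R² 17% (+7.5).
- 37.9% v 20%: 81.1%, then 83.2% (+2.1) and 88.2% (+7.1).
- 44.4% v 20%: 97.5%, then 98.1% (+0.6) and 99.1% (+1.6).

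The second and third lines share a saline rate but differ in gain. The distance from the power ceiling governs the gain, not the saline rate as such.

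**4. Simulated gain.** Two definitions of strength were used, and they are not identical: odds ratios per covariate (opioid use; VAS and ODI per SD), and R².

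- *Not prognostic.* −1.0 to 0 with logistic or standardised estimators at 0.9875. −1.3 at 44.4% v 26% with a Bayesian logistic model at a recalibrated 0.989. A further simulation went to about −3.
- *Moderate (OR 1.5 each, or R² about 5%).* +2.7 at 44.4% v 26% (+0.4 if VAS and ODI act in opposite directions); +1.0 to +1.8 at 37.9% v 20%; up to about +4 in the further simulation.
- *Strong (OR 2 each, or R² about 17%).* +8.6 at 44.4% v 26% (+3.6 if opposing); +5.5 to +6.1 at 37.9% v 20%; +7 to +9 in the further simulation.
- *Opioid use alone (OR 2).* Power 0.790 becomes 0.787. Nearly all of the gain comes from VAS and ODI.
- *The definitional link alone, primary.* −1.7 to +0.5 points over 15–30% saline.

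**5. Where Phase 2 points.** Section 1.6.3 gives p = 0.044 and p = 0.090 against saline. A saline result of 2/17 = 11.8% reproduces both by two-sided Fisher test (0.0441 and 0.0904); near matches lie at about 11–20%. This is an inference, because the saline denominator and the test are not shown. At 11.8% saline and 44.4% active, power is 99.99%.

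**6. Error of the adjusted model.** At 0.9875 the Bayesian logistic model's family-wise error was 0.0239–0.0276, so the limit can be breached. At 0.989 it was 0.0211–0.0245. Neither run included interim looks or imputation.

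**The case against.** The strongest reply is that nothing is broken. The test controls error, 9.6.2 gives a reason for it, and choosing between valid estimators is partly preference. If Phase 2 repeats, power is already near 100% and nothing is gained. Prognostic strength is undocumented, and the one mechanism visible in the documents, the endpoint definition, yields almost nothing on the primary. Adjustment also needs a new threshold. All of this stands, and it is why the priority is low.

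It does not remove the point. The Phase 2 active rate rests on 27 subjects (exact 95% interval 25% to 65%). With the other dose's 37.9% against 20% saline, power is about 81% and there is room to gain.

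Four stronger readings are tempting and not supported:

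- *Ignoring a randomisation stratum invalidates the test.* Step 1 shows the opposite: it is slightly conservative.
- *The trial should expect a large gain because saline will respond at 26–30%.* No passage supports that rate; the Phase 2 p-values point lower.
- *A saline rate of 20% or less caps the gain at about 2 points.* That holds for 44.4% active, where power is at least 97%, but not for smaller effects.
- *The plan never adjusts.* The SAP detail is not in the public text, so an adjusted sensitivity analysis cannot be excluded. Section 9.9 imputes from available information, so baseline values may enter there, although that would not adjust the comparison of observed outcomes.

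**Conclusion.** The point holds as a low-priority efficiency improvement to a valid analysis. At 120 per arm and 0.9875, where unadjusted power is about 80%, adjustment changes power by:

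- about 0 to −3 points if the covariates are not prognostic;
- +1 to +4 if moderate;
- +6 to +9 if strong and acting in the same direction, and about half that if VAS and ODI oppose each other.

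The ranges reflect estimator and threshold. Where power is already 97% or more, the gain is at most about 2 points.

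These figures rest on an assumed saline rate, an assumed primary threshold, assumed prognostic strengths and complete outcomes. Baseline may matter more for secondaries 4 and 5, but they are formally tested only after the primary and secondaries 1–3 succeed in that arm.

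**What to change.** 1. Estimate the prognostic strength of opioid use, baseline VAS and baseline ODI in the sponsor's Phase 2 data or in blinded pooled data. If the odds ratios are below about 1.5 per SD, keep the Beta test as primary and report an adjusted model as a sensitivity analysis.
2. Otherwise, before any interim analysis or unblinding, pre-specify a Bayesian logistic model of response on arm, opioid use, baseline VAS and baseline ODI with weakly informative priors. Standardise it to the marginal rate difference from saline and pool posterior draws over the same imputed datasets. No p-values are combined, so the rationale in 9.6.2 is kept.
3. Do not carry over 0.9875. Set the threshold by simulation that includes the imputation and any interim looks, so that family-wise one-sided error stays below 0.025.
4. Use the model for the primary and binary secondaries 1–5, and keep the Beta(0.5, 0.5) comparison as a sensitivity analysis.
5. State why site is not in the model. With up to 45 centres, 360/45 = 8 subjects each, leaving it out is defensible but should be explained.

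Cost: SAP text, a calibration simulation and a small power loss if the covariates prove not to be prognostic. No new data or subjects are needed.

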9.6.3 Secondary and Other Efficacy Analyses

The same Bayesian methodology used for the primary analysis will also be used for the secondary endpoints. The Bonferroni-adjusted posterior probability threshold of 0.9875 will apply to any subsequent secondary analyses performed.

As part of the gatekeeper strategy, the evaluation will be carried out in a hierarchical fashion following the order given below. Specifically, if the primary endpoint objective is met, the secondary outcomes will be evaluated hierarchically within each arm using the posterior probability threshold of 0.9875 for each comparison, sequentially. Once a key secondary endpoint is not met at this threshold within an arm, all subsequent comparisons in that arm will be considered exploratory.

- Pain Responder at both 12 AND 24 months: Measured as subjects meeting at least a 50% decrease from baseline in low back pain VAS score (average pain over 24 hours) at both Study Visit 6 (12 months post-treatment) and Study Visit 8 (24 months posttreatment) with no adjudicated post-treatment intervention through Study Visit 8.
- Functional Responder at both 12 AND 24 months: Measured as subjects meeting at least a 15-point decrease from baseline in ODI at both Study Visit 6 (12 months posttreatment) and Study Visit 8 (24 months post-treatment) with no adjudicated posttreatment intervention through Study Visit 8.
- 3. Treatment Success at 24 months: Measured as subjects meeting each of the following criteria at Study Visit 8 (24 months post-treatment):
 - a. at least a 50% reduction from baseline in low back pain VAS score (average pain over 24 hours); AND
 - b. at least a 15 point decrease from baseline ODI score; AND
 - c. no interventions at the treated level
- 4. Minimal Pain Responder at 24 Months: Measured as subjects meeting low back pain VAS score (average pain over 24 hours) of 20mm or less at Study Visit 8 (24 months post-treatment) with no adjudicated post-treatment intervention through Study Visit 8.
- 5. Minimal Disability Responder at 24 Months: Measured as subjects having an ODI score of 20% or less at Study Visit 8 (24 months post-treatment) with no adjudicated post-treatment intervention through Study Visit 8.
- 6. Time to first intervention over 24 months: Measured as time to first post-treatment intervention at the treated level through 24 months post-treatment.

CONFIDENTIAL

Mesoblast

For the time to first intervention (since study injection), a Kaplan-Meier analysis will be used. The overall treatment comparison and each active treatment group versus the saline control group, as well as between the two active treatment groups for time to first adjudicated intervention will be analysed using a log-rank test, stratified by study (or pooled) sites. The following Kaplan-Meier point estimates of time to first adjudicated intervention and their corresponding 95% confidence intervals (CI) will be presented: 25th percentile, median, and 75th percentile. Kaplan-Meier curves to illustrate the differences among the treatment arms will be provided. Subjects who did not receive post-treatment intervention and subjects who withdraw or are lost to follow-up will be censored at the last performed visit

CONFIDENTIAL

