The primary efficacy objective of the study is to demonstrate that either rexlemestrocel-L alone or rexlemestrocel-L + HA has a higher rate of treatment success — defined as a 50% reduction in low back pain VAS score, 15 point decrease in ODI score, and no interventions at the index level — compared to the saline control arm at 12 AND 24 months post-treatment. The significance level for the Primary Efficacy Endpoint is adjusted for multiple comparisons of each active arm to the control group. The family-wise type I error rate will be controlled below 0.025. Additional details, including the adjusted threshold for success, are provided in the SAP.
For all secondary endpoints, a gatekeeping strategy will be used maintain the overall type 1 error at overall one-sided 0.025. For all other exploratory efficacy endpoints, a two-sided significance level of 0.05 will be used for comparison between each active arm and the control group.
Sample Size and Randomization Approximately 360 subjects will be enrolled in a randomization ratio of 1:1:1, with each subject assigned to the rexlemestrocel-L alone, rexlemestrocel-L + HA, or saline control group. Randomization will be stratified by study site and opioid use at baseline (opioid users vs opioid non-users).

[figure not shown]

[figure not shown]
The per-protocol (PP) analysis set will contain all subjects in the ITT who received treatment to which they were randomized, had at least 1 post-treatment efficacy measurement (VAS and ODI), and did not experience any major protocol deviations.
Protocol deviations will be determined for all randomized subjects mainly from the clinical database and Clinical Trial Management System (CTMS) following clinical and/or medical review of subject data for relevant findings that might have an impact on the definition of the PP analysis set/ major protocol violations. Protocol deviations that occur during the study will be adjudicated by the sponsor (or designee) and categorized by severity. Protocol deviations will be classified as minor or major during a blinded review of the data prior to the lock of the database for analysis. If relevant deviations are identified, they will be designated as major protocol violations.
Safety Analysis Set The safety analysis set will contain all subjects who were randomized and received treatment, and subjects will be classified according to the actual treatment received. Safety analysis set will be used for the safety analyses.

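### As worded, one arm's primary win opens the secondary hierarchy in both active arms, so the stated overall one-sided 0.025 is not guaranteed in every null configuration

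*Combined protocol and SAP*

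**What the plan says.** Section 9.1 sets a study-level primary objective: "The primary efficacy objective of the study is to demonstrate that either rexlemestrocel-L alone or rexlemestrocel-L + HA has a higher rate" of success than saline. For the secondaries it makes a claim about error: "For secondary endpoints, a gatekeeping strategy will be used to maintain the overall type 1 error at overall one-sided 0.025". The synopsis makes the same claim.

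The condition for starting the secondaries appears in three places. Section 9.6.3, and the synopsis in the same words, says "if the primary endpoint objective is met, the secondary outcomes will be evaluated hierarchically within each arm using the posterior probability threshold of 0.9875". Section 9.4.2 says "If the primary analysis yields a significant result, then analyses will be performed on the following secondary efficacy endpoints in sequential order". None of the three says that an arm must have met its own primary. The only stop that works arm by arm in the readable text is triggered by a failed secondary: "Once a key secondary endpoint is not met at this threshold within an arm, all subsequent comparisons in that arm will be considered exploratory".

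Two things point the other way. Section 9.6.2 compares each active arm with saline separately and declares superiority arm by arm. Part of the multiplicity detail is also left to the SAP: section 9.1 says "Additional details, including the adjusted threshold for primary analysis success, will be finalized in the SAP", and the synopsis says "Additional details, including the adjusted threshold for success, are provided in the SAP".

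**The concern.** The two arms share 0.025 equally, 0.0125 each. A fixed sequence within an arm uses no more than that arm's 0.0125, provided the sequence starts with the arm's own primary. If a win in arm A also opens arm B's sequence after arm B has failed its primary, arm B gets a second chance of a false claim that the split does not pay for.

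Two things are at stake. The overall error level that the protocol claims may not hold. And an arm that failed the composite primary could still make a confirmatory claim on pain or function. A reader who has only the protocol cannot tell which rule applies.

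**Working it through.** **Inputs from the documents.** Overall one-sided 0.025 (section 9.1); secondary threshold 0.9875 (section 9.6.3); Beta(0.5, 0.5) priors (section 9.6.2); about 120 subjects per arm (section 3.1).

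**Assumptions.** Primary threshold 0.9875 (the value is deferred to the SAP), complete data, no interim looks. Control rates: composite 20-30%, pain 25-50%, function 35-55%.

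**The plan's own figure.** 2 x (1 - 0.9875) = 2 x 0.0125 = 0.025. It reproduces as the nominal bound for two parallel sequences.

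**Nominal bounds under the literal gate.**
1. Both primaries null: the gate opens only after an error already counted, so at most 2 x 0.0125 = 0.025.
2. Both primaries truly effective: one first null per arm, so at most 0.025.
3. Arm A effective on everything, arm B null: arm B's primary plus its first secondary, so at most 0.025.
4. Arm A effective on the primary but null on a later secondary, arm B null: arm A's null secondary, arm B's primary and arm B's first secondary, so 3 x 0.0125 = 0.0375 (1 - 0.9875^3 = 0.0370 if independent).

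With an own-arm gate each arm is a single fixed sequence at 0.0125, and the bound is 0.025 in all four cases.

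**Simulation of the actual rule** (reject if the posterior probability exceeds 0.9875; Monte Carlo standard error about 0.0002 to 0.0003).

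- Case 1: 0.023-0.024 under both gates.
- Case 3: arm B's error rises from about 0.013 to 0.017-0.023 as arm A's gain goes from +10 to +20 points. The total stays below 0.025. Arm B makes a pain claim after failing its own primary in 0.4-1.0% of trials.
- Case 4, arm A null on function, with equal gains on composite and pain:

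| Arm A gain (points) | Arm A power on primary | Literal gate | Own-arm gate |
|---|---|---|---|
| +5 | 8-10% | 0.016-0.023 | 0.014-0.021 |
| +10 | 27-33% | 0.023-0.028 | 0.017-0.024 |
| +15 | 57-65% | 0.030-0.031 | 0.021-0.024 |
| +20 | 83-88% | 0.031-0.033 | 0.023-0.025 |

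At +10 the literal gate exceeds 0.025 in 5 of 7 settings. With arm A's composite at 44.4% (the earlier-study rate in section 1.6.3, used only as a reference), the figures are 0.029-0.034 against 0.022-0.024.

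- Case 4, arm A null on pain instead: 0.022-0.026 against 0.021-0.024 at +5, and 0.027-0.029 against 0.023-0.025 at +10.

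A separate simulation of case 4 (control composite 20%, pain and function 40%) gave 0.0325 against 0.0244 with arm A null on pain (primary power 0.884). With arm A null only on a late, unrelated stand-in endpoint, it gave 0.0340 against 0.0245 (power 0.997) and 0.0254 against 0.0165 (power 0.65).

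**Sensitivity** (arm A null on function; primary threshold 0.990, or 100 per arm). At +10: 0.020-0.027 against 0.015-0.023. With arm A's composite at 44.4%: 0.027-0.035 against 0.019-0.026.

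**The case against.** **The own-arm reading is natural.** Superiority is declared arm by arm, testing is organised within each arm, and an equal Bonferroni split fits two sequences each headed by its own primary. This stands as a plausible reading. It does not remove the problem, because the condition in section 9.6.3 names the study-level objective and section 9.4.2 names no arm.

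**The SAP may settle it.** This also stands. A reader might infer that the plan lacks an own-arm gate, or that the final analysis will inflate error. The documents support neither: multiplicity detail is deferred to an SAP whose text cannot be read here. But section 9.6.3 itself sets out the procedure, with threshold, order and stop rule, so its wording should be unambiguous.

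**The excess needs an unusual mix of truths.** Both active arms deliver the same nominal cell dose (section 3.2), yet one must work and the other be null, with the working arm exactly null on a later step. Some simulated settings are also extreme: arm A's composite rate equals its function rate, so every function responder is also a pain responder. This limits how much weight the largest figures can carry. The excess does not depend on those settings. At +20, with composite below function (40% v 45%, 45% v 50%, 45% v 55%), the literal gate gives 0.0328, 0.0320 and 0.0319, against 0.0233, 0.0234 and 0.0226.

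**The protocol promises an overall level, not control in every configuration.** That is literally so. But at the global null the two gates perform alike, so a gatekeeping claim has content only for configurations in which some primary is truly effective.

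**The benchmark is approximate.** The exact size of a single test at 120 per arm is 0.0118-0.0135 for rates of 10-50%, so the own-arm gate restores nominal control only. The gap between the two gates is not explained by test size, which is common to both.

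**Conclusion.** The point holds as a finding about the protocol's wording. The literal rule would test the secondaries of an arm that failed its own primary, and it does not guarantee the stated one-sided 0.025.

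The excess is confined to mixed nulls: one arm effective on the primary with a null later secondary, and the other arm null. There the nominal bound is 0.0375. Simulated error is about 0.026-0.033 for moderate to large assumed effects, with individual settings from 0.023 to 0.034 at 120 per arm and a threshold of 0.9875. The own-arm gate gives at most about 0.025 in the same settings.

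A general loss of type I error control would be the wrong inference. There is no excess under the global null or when the working arm works on every endpoint, and generally none at small effects. The sizes rest on assumed response rates, an assumed primary threshold, complete data and no interim looks. The point should be fixed, with medium confidence, because the SAP may already contain the rule.

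**What to change.** In the synopsis, section 9.4.2 and section 9.6.3, write: *Secondary endpoints are tested for an active arm only if that arm has itself met the primary endpoint threshold versus saline; they are then tested in the stated order within that arm at posterior probability 0.9875.* If the SAP already says this, cite it in those places instead.

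The cost is wording only, with no change to sample size or data collection. The downside is that an arm that fails its primary can make no confirmatory secondary claim, even when the other arm succeeds.
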